#### 2 STUDY OBJECTIVES

## 2.1 Primary Objectives

#### **Cohort A Substudy (≥65 Years)**

To evaluate the humoral immune responses of mRNA-1083 for noninferiority relative to active comparators against vaccine matched strains for influenza and SARS-CoV-2 at Day 29.

To evaluate the safety and reactogenicity of study injections across treatment arms.

#### Cohort B Substudy (≥50 to <65 Years)

To evaluate the humoral immune responses of mRNA-1083 for noninferiority relative to active comparators against vaccine-matched strains for influenza and SARS-CoV-2 at Day 29.

To evaluate the safety and reactogenicity of study injections across treatment arms.

## 2.2 Secondary Objectives

#### **Cohort A Substudy (≥65 Years)**

To further evaluate the humoral immune response of mRNA-1083 for superiority relative to active comparators against vaccine-matched strains for influenza and SARS-CoV-2 at Day 29.

To evaluate the humoral immune responses to vaccine matched strains for influenza and SARS-CoV-2 across treatment arms at Day 29.

To evaluate the humoral immune responses for influenza across treatment arms at Day 29 using the microneutralization assay.

#### Cohort B Substudy (≥50 to <65 Years)

To further evaluate the humoral immune response of mRNA-1083 for superiority relative to active comparators against vaccine-matched strains for influenza and SARS-CoV-2 at Day 29.

To evaluate the humoral immune responses to vaccine matched strains for influenza and SARS-CoV-2 across treatment arms at Day 29.

To evaluate the humoral immune responses for influenza across treatment arms at Day 29 using the microneutralization assay.

# 2.3 Exploratory Objectives

The following exploratory objectives may be performed:

### **Cohort A Substudy (≥65 Years)**

To evaluate the humoral immune responses to vaccine matched strains for influenza and SARS-CoV-2 across treatment arms at all evaluable humoral immunogenicity time points.

To evaluate the humoral immune responses to vaccine mismatched strains for influenza and SARS-CoV-2 across treatment arms.

To characterize other health outcomes during the first 7 days after study injections.

#### Cohort B Substudy (≥50 to <65 Years)

To evaluate the humoral immune responses to vaccine-matched strains for influenza and SARS-CoV-2 across treatment arms at all evaluable humoral immunogenicity time points.

To evaluate the humoral immune responses to vaccine-mismatched strains for influenza and SARS-CoV-2 across treatment arms.

To characterize other health outcomes during the first 7 days after study injections.

#### 3 STUDY ENDPOINTS

## 3.1 Primary Endpoints

#### **Cohort A Substudy (≥65 Years)**

GM level at Day 29 by HAI assay for influenza and by PsVNA for SARS-CoV-2.

Influenza: Percentage of participants with seroconversion, defined as a Day 29 post injection level ≥1:40 if Baseline is <1:10 or a 4 fold or greater rise if Baseline is ≥1:10 in anti-HA antibodies measured by HAI assay.

SARS-CoV-2: Percentage of participants with seroresponse, defined as a Day 29 post-injection level ≥4-fold rise if Baseline is ≥ LLOQ or ≥4×LLOQ if Baseline value is <LLOQ in the nAb values measured by PsVNA.

Solicited local and systemic ARs through 7 days after study injection.

Unsolicited AEs through 28 days after study injection.

MAAEs from Day 1 through Day 181 (Month 6) or EoS.

AESIs from Day 1 through Day 181 (Month 6) or EoS.

SAEs from the time of informed consent through Day 181 (Month 6) or EoS.

AEs leading to discontinuation from Day 1 through Day 181 (Month 6) or EoS.

#### Cohort B Substudy (≥50 to <65 Years)

GM level at Day 29 by HAI assay for influenza and by PsVNA for SARS-CoV-2.

Influenza: Percentage of participants with seroconversion, defined as a Day 29 post injection level ≥1:40 if Baseline is <1:10 or a 4 fold or greater rise if Baseline is ≥1:10 in anti HA antibodies measured by HAI assay.

SARS-CoV-2: Percentage of participants with seroresponse, defined as a Day 29 post injection level ≥4 fold rise if Baseline is ≥LLOQ or ≥4×LLOQ if Baseline value is <LLOQ in the nAb values measured by PsVNA.

Solicited local and systemic ARs through 7 days after each study injection.

Unsolicited AEs through 28 days after each study injection.

MAAEs from Day 1 through Day 181 (Month 6) or EoS.

AESIs from Day 1 through Day 181 (Month 6) or EoS.

SAEs from the time of informed consent through Day 181 (Month 6) or EoS.

AEs leading to discontinuation from Day 1 through Day 181 (Month 6) or EoS.

## 3.2 Secondary Endpoints

#### **Cohort A Substudy (≥65 Years)**

GM level at Day 29 by HAI assay for and by PsVNA for SARS-CoV-2.

- Influenza: Percentage of participants with seroconversion, defined as a Day 29 post-injection level ≥1:40 if Baseline is <1:10 or a 4-fold or greater rise if Baseline is ≥1:10 in anti-HA antibodies measured by HAI assay.
- SARS-CoV-2: Percentage of participants with seroresponse, defined as a Day 29 post-injection level ≥4-fold rise if Baseline is ≥LLOQ or ≥4 × LLOQ if Baseline value is <LLOQ in the nAb values measured by PsVNA
- GMFR at Day 29 compared with Day 1 by HAI assay for influenza and by PsVNA for SARS-CoV-2.
- GM level at Day 29 and GMFR at Day 29 compared with Day 1 by microneutralization assay for influenza.

### **Cohort B Substudy (≥50 to <65 Years)**

- GM level at Day 29 by HAI assay for influenza and by PsVNA for SARS-CoV-2.
- Influenza: Percentage of participants with seroconversion, defined as a Day 29 post injection level ≥1:40 if Baseline is <1:10 or a 4 fold or greater rise if Baseline is ≥1:10 in anti HA antibodies measured by HAI assay.
- SARS-CoV-2: Percentage of participants with seroresponse, defined as a Day 29 post injection level ≥4 fold rise if Baseline is ≥LLOQ or ≥4×LLOQ if Baseline value is <LLOQ in the nAb values measured by PsVNA.
- GMFR at Day 29 compared with Day 1 by HAI assay for influenza and by PsVNA for SARS-CoV-2.
- GM level at Day 29 and GMFR at Day 29 compared with Day 1 by microneutralization assay for influenza.

## 3.3 Exploratory Endpoints

The following exploratory endpoints may be performed:

#### **Cohort A Substudy (≥65 Years)**

- GM level and GMFR at all evaluable time points compared with Day 1 by HAI for vaccine matched strains of and by PsVNA for vaccine matched strains of SARS-CoV-2.
  - Influenza: Percentage of participants with seroconversion, as defined in Section 3.1.
  - SARS-CoV-2: Percentage of participants with seroresponse, as defined in Section 3.1.
- GM level and GMFR at all evaluable time points compared with Day 1 by HAI for vaccine mismatched strains of influenza and by PsVNA for vaccine mismatched strains of SARS-CoV-2.
  - Influenza: Percentage of participants with seroconversion, as defined in Section 3.1.

 SARS-CoV-2: Percentage of participants with seroresponse, as defined in Section 3.1.

Describe EQ-5D-5L health questionnaire utility score through 7 days after study injection.

### **Cohort B Substudy (≥50 to <65 Years)**

- GM level and GMFR at all evaluable time points compared with Day 1 by HAI for vaccine matched strains of influenza and by PsVNA for vaccine matched strains of SARS-CoV-2.
  - Influenza: Percentage of participants with seroconversion, as defined in Section 3.1.
  - SARS-CoV-2: Percentage of participants with seroresponse, as defined in Section 3.1.
- GM level and GMFR at all evaluable time points compared with Day 1 by HAI for vaccine mismatched strains of influenza and by PsVNA for vaccine mismatched strains of SARS-CoV-2.
  - Influenza: Percentage of participants with seroconversion, as defined in Section 3.1.
  - SARS-CoV-2: Percentage of participants with seroresponse, as defined in Section 3.1.
- Describe EQ-5D-5L health questionnaire utility score daily from Day 1 through 7 days after study injection.
- Describe WPAI: GH v2.0 impairment percentages for absenteeism, presenteeism, work productivity loss, and activity impairment through 7 days after study injection.

#### 4 STUDY DESIGN

## 4.1 Overall Study Design

This study will be a Phase 3, randomized, stratified, observer-blind, active-control study conducted in 2 age-group substudies (Cohort A and Cohort B). This clinical study consists of 2 separate substudies:

[figure not shown]
Cohort A will evaluate the safety, reactogenicity, and immunogenicity of the 40 µg mRNA 1083 vaccine and dose level as compared with co administered active licensed comparator vaccines (Fluzone® HD and Spikevax) in healthy adults ≥65 years of age.

Cohort B will evaluate the safety, reactogenicity, and immunogenicity of the 40  $\mu$ g mRNA 1083 vaccine and dose level as compared with co administered active licensed comparator vaccines (Fluarix® and Spikevax) in healthy adults 50 to <65 years of age.

Each of the 2 independent substudies has its own separate hypotheses and statistical analyses, and its own multiplicity control for overall Type I error rate (2-sided alpha of 5%) for the co-primary endpoints within the substudy.

Overall, the study will enroll approximately 8000 participants with approximately 4000 participants (in a 1:1 ratio) in Cohort A and approximately 4000 participants (in a 1:1 ratio) in Cohort B. The study schema is presented in Figure 1.

Figure 1 Study Schematic and Participant Disposition

On Day 1, each participant will receive 2 injections administered IM, 1 in each deltoid. The interventions administrated are described in Table 1.

Table 1 Study Arms and Interventions Administered

Substudies	Arm Titles	Arm Types	Arm Descriptions
Cohort A (≥65 years of age)	mRNA 1083 + Placebo n=2000	Experimental	Participants will receive mRNA 1083 (40 µg) and Placebo, administered as IM injections, 1 in each deltoid muscle on Day 1.
Sı	Fluzone HD + Spikevax n=2000	Active Comparator	Participants will receive Fluzone HD and Spikevax administered as IM injections, 1 in each deltoid muscle on Day 1.
Cohort B (50 to <65 years of age)	mRNA-1083 + Placebo n=2000	Experimental	Participants will receive mRNA-1083 (40 µg) and Placebo, administered as IM injections, 1 in each deltoid muscle on Day 1.
n=4000	Fluarix + Spikevax n=2000	Active Comparator	Participants will receive Fluarix and Spikevax, administered as IM injections, 1 in each deltoid muscle on Day 1.

Study details include:

Study duration: approximately 6 months, including the Screening period.

Treatment duration: Study injections are scheduled for all participants on Day 1 (Baseline).

#### Visit frequency:

- All participants will have scheduled in person clinic visits for Screening and on Day 1 (Baseline) and Day 29 (Month 1).
- All participants will have a safety follow up call on Days 8 and 91 (Month 3).
- On Day 181 (Month 6), at least 800 participants per substudy cohort will have an in-person clinic visit for sample collection. All remaining participants will have a safety follow up call.

For a more detailed presentation of the study, please refer to the Schedule of Activities (SoA) available in Appendix A.

## 4.2 Statistical Hypotheses

Each of the 2 independent substudies, Cohort A (65 years or greater) and Cohort B (50 to <65 years of age), has its own separate hypotheses and statistical analyses, and its own multiplicity control for overall Type I error rate (2-sided alpha of 5%) for the co-primary endpoints within the substudy. Each of the 2 substudies has the co-primary immunogenicity endpoints as described below.

#### **4.2.1** Hypotheses in Cohort A Substudy (≥65 Years)

There are six statistical hypotheses for the substudy that will be tested sequentially according to the procedures described below:

#### 4.2.1.1 Co-primary Hypotheses

Each of the primary immunogenicity endpoints will be evaluated for noninferiority of mRNA-1083 (40  $\mu$ g) + Placebo versus Fluzone HD + Spikevax at a 2-sided alpha of 0.025 level for Cohort A for adults aged 65 years or greater. The first two null hypotheses H0 and H0 will be tested simultaneously, as below.

The success criteria of noninferiority on the five co-primary endpoints for GM level are met if  $H^{1}_{0}$  is rejected at two-sided 0.025 level. Similarly, the success criteria of noninferiority on the five co-primary endpoints for SCR or SRR are met if  $H^{2}_{0}$  is rejected at two-sided 0.025 level.

#### Five Co-primary Endpoints Based on Influenza and SARS-CoV-2 GM level at Day 29

The null hypothesis H¹₀: for each of the 4 influenza strains (2 A strains: H1N1, H3N2 and 2 B strains: Victoria, Yamagata) and 1 SARS-CoV-2 strain (Omicron XBB.1.5), the immunogenicity response to mRNA-1083 (40 μg) + Placebo, as measured by GM level at Day 29 using HAI assay for influenza and PsVNA for SARS-CoV-2, is inferior compared with that in participants who received Fluzone HD + Spikevax.

The NI in GM level in participants who received mRNA-1083 (40  $\mu$ g) + Placebo compared with that of participants who received Fluzone HD + Spikevax will be demonstrated by the lower bound of the two-sided 97.5% CI of the GMR ruling out 0.667 (lower bound >0.667) using a

NIM of 1.5. The GMR is defined as the ratio of the GM level of HAI or PsVNA in those participants receiving mRNA-1083 (40  $\mu$ g) + Placebo versus the GM level of those participants receiving Fluzone HD + Spikevax.

#### Five Co-primary Endpoints Based on Influenza SCR or SARS CoV-2 SRR at Day 29

The null hypothesis H0: for each of the 4 influenza strains (2 A strains: H1N1, H3N2 and 2 B strains: Victoria, Yamagata) and the SARS-CoV-2 strain (Omicron XBB.1.5), the immunogenicity response in participants who received mRNA-1083 (40 μg) + Placebo, as measured by Day 29 SCR using HAI assay (for influenza strains) or SRR using PsVNA (for SARS-CoV-2), is inferior compared with that in participants who received Licensed Fluzone HD + Spikevax.

The NI in SCR or SRR in participants who received mRNA-1083 ( $40 \mu g$ ) + Placebo compared with that of participants who received Fluzone HD + Spikevax will be demonstrated by the lower bound of the two-sided 97.5% CI of the SCR or SRR difference at Day 29 ruling out -10% (lower bound >-10%) using a NIM of 10%.

For influenza, the SCR at Day 29 is defined as the proportion of participants with either a preinjection HAI level  $\leq$ 1:10 and a postinjection HAI level  $\geq$ 1:40, or a preinjection HAI level  $\geq$ 1:10 and a minimum 4-fold rise in postinjection HAI antibody level. The SCR difference Day 29 is defined as the difference between the SCR at Day 29 among those participants receiving mRNA-1083 (40 µg) + Placebo and the SCR at Day 29 among those participants receiving Fluzone HD + Spikevax.

For SARS-CoV-2, the SRR at Day 29 is defined as the proportion of participants with either GMFR in nAb levels of  $\geq$ 4-fold postinjection compared with Day 1 in those with Baseline level  $\geq$ LLOQ, or postinjection level  $\geq$ 4×LLOQ if Baseline level is <LLOQ. The SRR difference at Day 29 is defined as the difference between the SRR at Day 29 among those participants receiving mRNA-1083 (40  $\mu$ g) + Placebo and the SRR at Day 29 among those participants receiving Fluzone HD + Spikevax.

### 4.2.1.2 Secondary Hypotheses

If the noninferiority success criteria of the coprimary endpoints for GM level are met, the following hypotheses will be tested sequentially to support secondary objectives:

The null hypothesis  $H^3_0$ : for each of the 4 influenza strains (2 A strains: H1N1, H3N2 and 2 B strains: Victoria, Yamagata), the immunogenicity response as measured using the GM level at Day 29 for the HAI assay for influenza, of mRNA-1083 (40 µg) + Placebo to Fluzone HD + Spikevax is not superior to Fluzone HD + Spikevax. The superiority in GM level in participants who received mRNA-1083 (40 µg) + Placebo compared to that of participants who received active comparator will be demonstrated by the lower bound of the (100%-  $\alpha_1$ ) CI of the GMR ruling out 1 (lower bound >1) for all 4 influenza strains. It will be tested at a two-sided  $\alpha_1$ =5% level if noninferiority is demonstrated for GM level ( $H^1_0$  rejected) and SCR or SRR ( $H^2_0$  rejected); and at a two-sided  $\alpha_1$ =2.5% level if non-inferiority is only demonstrated for GM level ( $H^1_0$  rejected).

If the superiority success criteria for GM levels at Day 29 using HAI assay for influenza are met  $(\underline{H^3_0}$  rejected), the null hypothesis  $\underline{H^4_0}$  will be tested: for the SARS-CoV-2 strain (Omicron

XBB.1.5), the immunogenicity response to mRNA-1083 (40  $\mu$ g) + Placebo, as measured by GM level at Day 29 using PsVNA is not superior to that in participants who received Fluzone HD + Spikevax. The superiority in GM level in participants who received mRNA-1083 (40  $\mu$ g) + Placebo compared to that of participants who received active comparator, will be demonstrated by the lower bound of the (100%-  $\alpha_1$ ) CI of the GMR ruling out 1 (lower bound >1). The same level  $\alpha_1$  will be passed to test hypothesis H0.

If the superiority success criteria for GM levels at Day 29 using PsVNA assay for SARS-CoV-2 are met ( $\underline{H^4}_0$  rejected), and noninferiority success criteria for SCR or SRR are met ( $\underline{H^2}_0$  rejected), the hypothesis  $\underline{H^5}_0$  will be tested. The null hypothesis  $\underline{H^5}_0$ : for each of the 4 influenza strains (2 A strains: H1N1, H3N2 and 2 B strains: Victoria, Yamagata), the immunogenicity response to mRNA-1083 (40  $\mu$ g) + Placebo, as measured by D29 SCR using HAI assay (for influenza strains), is not superior to that in participants who received Fluzone HD + Spikevax. The superiority in SCR in participants who received mRNA-1083 (40  $\mu$ g) + Placebo compared to that of participants who received active comparator will be demonstrated by the lower bound of the 95% CI of the SCR difference ruling out 0% (lower bound >0%) for all 4 influenza strains.

If the superiority success criteria for SCR at Day 29 using HAI assay for influenza are met ( $\underline{H}^5_0$  rejected), the hypothesis  $\underline{H}^6_0$  will be tested. The null hypothesis  $\underline{H}^6_0$ : for the SARS-CoV-2 strain (Omicron XBB.1.5), the immunogenicity response to mRNA-1083 (40  $\mu$ g) + Placebo, as measured by Day 29 SRR using PsVNA (for SARS-CoV-2) is not superior to that in participants who received Fluzone HD + Spikevax. The superiority in SRR in participants who received mRNA-1083 (40  $\mu$ g) + Placebo compared to that of participants who received active comparator will be demonstrated by the lower bound of the 95% CI of the SRR difference ruling out 0% (lower bound >0%).

#### 4.2.2 Hypotheses in Cohort B Substudy (≥50 to <65 Years)

There are six statistical hypotheses for the substudy that will be tested according to the procedures described below:

#### 4.2.2.1 Co-primary Hypotheses

Each of the primary immunogenicity endpoints will be evaluated for noninferiority of mRNA-1083 (40  $\mu$ g) + Placebo versus Fluarix + Spikevax at a 2-sided alpha of 0.025 level for Cohort B for adults aged  $\geq$ 50 to <65 years. The first two null hypotheses H $^1$ 0 and H $^2$ 0 will be tested simultaneously, as below.

The success criteria of noninferiority on the five co-primary endpoints for GM level are met if  $H^{1}_{0}$  is rejected at two-sided 0.025 level. Similarly, the success criteria of noninferiority on the five co-primary endpoints for SCR or SRR are met if  $H^{2}_{0}$  is rejected at two-sided 0.025 level.

### Five Co-primary Endpoints Based on Influenza and SARS-CoV-2 GM Level at Day 29

The null hypothesis H¹₀: for each of the 4 influenza strains (2 A strains: H1N1, H3N2 and 2 B strains: Victoria, Yamagata) and 1 SARS-CoV-2 strain (Omicron XBB.1.5), the immunogenicity response in participants who received mRNA-1083 (40 μg) + Placebo, as measured by GM level at Day 29 using HAI assay for influenza and PsVNA for SARS-CoV-2, is inferior compared with that in participants who received Fluarix + Spikevax.

The NI in GM level in participants who received mRNA-1083 (40  $\mu$ g) + Placebo compared with that of participants who received Fluarix + Spikevax will be demonstrated by the lower bound of the two-sided 97.5% CI of the GMR ruling out 0.667 (lower bound >0.667) using a NIM of 1.5. The GMR is defined as the ratio of the GM level of HAI or PsVNA in those participants receiving mRNA-1083 (40  $\mu$ g) + Placebo versus the GM level of those receiving Fluarix + Spikevax.

#### Five Co-primary Endpoints Based on Influenza SCR or SARS CoV-2 SRR at Day 29

The null hypothesis H0: for each of the 4 influenza strains (2 A strains: H1N1, H3N2 and 2 B strains: Victoria, Yamagata) and the SARS-CoV-2 strain (Omicron XBB.1.5), the immunogenicity response in participants who received mRNA-1083 (40 μg) + Placebo, as measured by Day 29 SCR using HAI assay (for influenza strains) or SRR using PsVNA (for SARS-CoV-2), is inferior compared with that in participants who received Fluarix + Spikevax.

The NI in SCR or SRR in those participants who received mRNA-1083 (40  $\mu$ g) + Placebo compared with that of those who received Fluarix + Spikevax will be demonstrated by the lower bound of the two-sided 97.5% CI of the SCR or SRR difference at Day 29 ruling out -10% (lower bound >-10%) using a NIM of 10%.

For influenza, the SCR at Day 29 is defined as the proportion of participants with either a preinjection HAI level <1:10 and a postinjection HAI level  $\geq$ 1:40, or a preinjection HAI level  $\geq$ 1:10 and a minimum 4-fold rise in postinjection HAI antibody level. The SCR difference Day 29 is defined as the difference between the SCR at Day 29 among those participants receiving mRNA-1083 (40  $\mu$ g) + Placebo and the SCR at Day 29 among those receiving Fluarix + Spikevax.

For SARS-CoV-2, the SRR at Day 29 is defined as the proportion of participants with either a GMFR in nAb levels of  $\geq$ 4-fold postinjection compared with Day 1 in those with Baseline level  $\geq$ LLOQ or postinjection level  $\geq$ 4×LLOQ if Baseline level is <LLOQ. The SRR difference at Day 29 is defined as the difference between the SRR at Day 29 among those participants receiving mRNA-1083 (40  $\mu$ g) + Placebo and the SRR at Day 29 among those receiving Fluarix + Spikevax.

### 4.2.2.2 Secondary Hypotheses

If the noninferiority success criteria of the coprimary endpoints for GM level are met, the following hypotheses will be tested sequentially to support secondary objectives:

The null hypothesis  $H^3_0$ : for each of the 4 influenza strains (2 A strains: H1N1, H3N2 and 2 B strains: Victoria, Yamagata), the immunogenicity response as measured using the GM level at Day 29 for the HAI assay for influenza, of mRNA-1083 (40 µg) + Placebo to Fluarix + Spikevax is not superior to Fluarix + Spikevax. The superiority in GM level in participants who received mRNA-1083 (40 µg) + Placebo compared to that of participants who received active comparator will be demonstrated by the lower bound of the (100%-  $\alpha_1$ ) CI of the GMR ruling out 1 (lower bound >1) for all 4 influenza strains. It will be tested at a two-sided  $\alpha_1$ =5% level if noninferiority is demonstrated for GM level (H0 rejected) and SCR or SRR (H0 rejected); and at a two-sided  $\alpha_1$ =2.5% level if non-inferiority is only demonstrated for GM level (H0 rejected).

If the superiority success criteria for GM levels at Day 29 using HAI assay for influenza are met  $(\underline{H^3}_0$  rejected), the null hypothesis  $\underline{H^4}_0$  will be tested: for the SARS-CoV-2 strain (Omicron XBB.1.5), the immunogenicity response to mRNA-1083 (40  $\mu$ g) + Placebo, as measured by GM level at Day 29 using PsVNA is not superior to that in participants who received Fluarix + Spikevax. The superiority in GM level in participants who received mRNA-1083 (40  $\mu$ g) + Placebo compared to that of participants who received active comparator will be demonstrated by the lower bound of the (100%-  $\alpha_1$ ) CI of the GMR ruling out 1 (lower bound >1). The same level  $\alpha_1$  will be passed to test hypothesis  $\underline{H^4}_0$ .

If the superiority success criteria for GM levels at Day 29 using PsVNA assay for SARS-CoV-2 are met ( $\underline{H^4_0}$  rejected), and noninferiority success criteria for SCR or SRR are met ( $\underline{H^2_0}$  rejected), the hypothesis  $\underline{H^5_0}$  will be tested. The null hypothesis  $\underline{H^5_0}$ : for each of the 4 influenza strains (2 A strains: H1N1, H3N2 and 2 B strains: Victoria, Yamagata), the immunogenicity response to mRNA-1083 (40 µg) + Placebo, as measured by Day 29 SCR using HAI assay (for influenza strains), is not superior to that in participants who received Fluarix HD + Spikevax. The superiority in SCR in participants who received mRNA-1083 (40 µg) + Placebo compared to that of participants who received active comparator will be demonstrated by the lower bound of the 95% CI of the SCR ruling out 0% (lower bound >0%) for all the 4 influenza strains.

If the superiority success criteria for SCR at Day 29 using HAI assay for influenza are met ( $\underline{H^5}_0$  rejected), the hypothesis  $\underline{H^6}_0$  will be tested. The null hypothesis  $\underline{H^6}_0$ : for the SARS-CoV-2 strain (Omicron XBB.1.5), the immunogenicity response to mRNA-1083 (40  $\mu$ g) + Placebo, as measured by Day 29 SRR using PsVNA (for SARS-CoV-2) is not superior to that in participants who received Fluarix + Spikevax. The superiority in SRR in participants who received mRNA-1083 (40  $\mu$ g) + Placebo compared to that of participants who received active comparator will be demonstrated by the lower bound of the 95% CI of the SRR difference ruling out 0% (lower bound >0%).

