mRNA-1083 (40 µg) + Placebo compared to that of participants who received active comparator will be demonstrated by the lower bound of the (100%- α_1) CI of the GMR ruling out 1 (lower bound >1). The same level α_1 will be passed to test hypothesis H⁴₀.

If the superiority success criteria for GM levels at Day 29 using PsVNA assay for SARS-CoV-2 are met (H^4_0 rejected), and noninferiority success criteria for SCR or SRR are met (H^2_0 rejected), the hypothesis H^5_0 will be tested. The null hypothesis H^5_0 : for each of the 4 influenza strains (2 A strains: H1N1, H3N2 and 2 B strains: Victoria, Yamagata), the immunogenicity response to mRNA1083 (40 μ g) + Placebo, as measured by Day 29 SCR using HAI assay (for influenza strains) is not superior to that in participants who received Fluarix HD + Spikevax. The superiority in SCR in participants who received mRNA1083 (40 μ g) + Placebo compared to that of participants who received active comparator will be demonstrated by the lower bound of the 95% CI of the SCR difference ruling out 0% (lower bound >0%) for all the 4 influenza strains.

If the superiority success criteria for SCR at Day 29 using HAI assay for influenza are met (${\rm H}^5{}_0$ rejected), the hypothesis ${\rm H}^6{}_0$ will be tested. The null hypothesis ${\rm H}^6{}_0$: for the SARS-CoV-2 strain (Omicron XBB.1.5), the immunogenicity response to mRNA-1083 (40 μ g) + Placebo, as measured by Day 29 SRR using PsVNA (for SARS-CoV-2) is not superior to that in participants who received Fluarix + Spikevax. The superiority in SRR in participants who received mRNA-1083 (40 μ g) + Placebo compared to that of participants who received active comparator will be demonstrated by the lower bound of the 95% CI of the SRR difference ruling out 0% (lower bound >0%).

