#### 1 INTRODUCTION

This statistical analysis plan (SAP), which describes the planned analyses for study mRNA-1083-P301, is based on the most recent approved clinical study protocol (CSP), dated 22-MAR-2024, and the most recent approved electronic case report form (eCRF), dated 18-OCT-2023.

In addition to the principal features of analyses for this study described in Section 9 of the protocol, this SAP provides statistical analysis details/data derivations. It also documents modifications or additions to the analysis plan that are not "principal" in nature and result from information that was not available at the time of protocol finalization.

Study mRNA-1083-P301 is a phase 3, randomized, observer-blind, active-control study to evaluate the safety, reactogenicity, and immunogenicity of mRNA-1083 (SARS-CoV-2 and influenza) vaccine in healthy adult participants ≥ 50 years of age.

PPD Biostatistics and Programming team, designee of Moderna Biostatistics and Programming department, will perform the statistical analysis of the safety, reactogenicity, immunogenicity and efficacy data; Statistical Analysis System (SAS) Version 9.4 or higher will be used to generate all statistical outputs (tables, figures, listings, and datasets). The SAP will be finalized and approved prior to the primary analysis clinical database lock and treatment unblinding for the study. If the methods in this SAP differ from the methods described in the protocol, the SAP will prevail.

In this document, study vaccination, intervention administration, injection of investigational product (IP)/ investigational vaccine, dosing, and injection are used interchangeably. Treatment group, investigational treatment arm, treatment arm are used interchangeably.

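### The Cohort B success criterion for SCR superiority (H5) in SAP 4.2.2.2 omits the word difference, so as written it does not test superiority; the between-arm difference is clearly meant and should be restored

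*SAP*

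**What the plan says.** H5 is the fourth step of the Cohort B testing sequence: superiority of mRNA-1083 + Placebo over Fluarix + Spikevax in Day 29 seroconversion, for all four influenza strains. SAP 4.2.2.2 gives the success criterion as the "lower bound of the 95% CI of the SCR ruling out 0% (lower bound >0%) for all the 4 influenza strains".

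The parallel texts put the criterion on the difference:

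- SAP 4.2.1.2, Cohort A, H5: "lower bound of the 95% CI of the SCR difference ruling out 0% (lower bound >0%) for all 4 influenza strains".
- Protocol 9.2, Cohort B, H5: "95% CI of the SCR difference ruling out 0% (lower bound >0%) for all the 4 influenza strains".
- SAP 4.2.2.2, Cohort B, H6, in the next paragraph: "95% CI of the SRR difference ruling out 0% (lower bound >0" percent.

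SAP 6.4 tests H5 at a two-sided 0.05 level, only after H4 and H2 have been rejected, and refers back to SAP 4.2 for the detail. SAP 1 adds: "If the methods in this SAP differ from the methods described in the protocol, the SAP will prevail". SAP 7 lists no changes from the protocol's planned analysis.

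**The concern.** SCR and SCR difference are separate quantities in this SAP. Section 4.2.2.1 defines each, and section 6.3.1.3 plans a 95% interval for each: Clopper-Pearson for the SCR within an arm, Miettinen-Nurminen for the difference. So the literal wording points to an output that will be produced, and that output does not compare the arms.

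The rest of the SAP text does not restate the rule. Section 6.4 gives only the level and the order of testing, and 6.3.1.3 gives only the noninferiority criterion. Figure 2 is not available in the text reviewed, so nothing is claimed about it. The protocol has the right wording, but the precedence clause means it does not automatically override the SAP.

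At stake is an alpha-controlled superiority claim in Cohort B and the gate to H6. H6 keeps its own valid criterion on the difference; what it would lose is the protection of a real test in front of it.

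**Working it through.** **Inputs.** SAP 4.3.2: about 2,000 per arm including about 15% drop-outs; planning rates 68% vs 70% (two A strains and SARS-CoV-2) and 58% vs 60% (two B strains); noninferiority margin 10 points at two-sided 0.025; GMR 0.85 with SD 1.5 on the natural log scale. SAP 6.4: H5 at two-sided 0.05. Evaluable per arm: 2,000 × 0.85 = 1,700, with the drop-out rate applied to both arms.

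**1. The plan's own figure.** Noninferiority power per strain is Φ[(0.10 − 0.02)/SE − 2.241], with SE = √[p₁(1−p₁)/n + p₂(1−p₂)/n].

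- 68% vs 70%: SE = 0.01586, so Φ(5.044 − 2.241) = 99.7%.
- 58% vs 60%: SE = 0.01687, so Φ(4.743 − 2.241) = 99.4%.
- Overall, treating strains as independent: 0.9975³ × 0.9938² = 98.0%. The stated figure of at least 95% is reproduced.

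**2. The H5 rule as written.** It is applied here to the mRNA-1083 arm with the Clopper-Pearson interval.

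| Seroconverters out of 1,700 | Lower 95% limit | Criterion met? |
|---|---|---|
| 0 | 0 | no |
| 1 | 1 − 0.975^(1/1700) = 0.0015% | yes |
| 986 (58%) | 55.6% | yes |
| 1,156 (68%) | 65.7% | yes |

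At the planning rates all four strains pass with probability 1 to machine precision, although each rate lies 2 points below its comparator.

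**3. The H5 rule as intended.** The probability that the lower 95% limit of the difference exceeds 0 is about Φ[(p₁ − p₂)/SE − 1.96] per strain.

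- Equal true rates: Φ(−1.96) = 2.5%.
- 68% vs 70%: Φ(−1.261 − 1.96) = 0.06%.
- 58% vs 60%: Φ(−1.186 − 1.96) = 0.08%.

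An observed gain of roughly 1.96 × √[2p(1−p)/1700] is needed: 3.1 points at p = 0.70 and 3.3 points at p = 0.60.

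**4. Whether the earlier steps stand in for the missing comparison.** H1, H3 and H4 concern GM levels. H2 concerns SCR and SRR but rules out only a 10-point deficit. Miettinen-Nurminen intervals for two possible observed results in one strain, 1,700 per arm:

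| Observed SCR | Interval for the difference | H2 for that strain | H5 as intended | H5 as written |
|---|---|---|---|---|
| 62% vs 60% | 95%: −1.3% to +5.3% | met | not met | met |
| 54% vs 60% | 97.5% lower limit: −9.8% | met | not met | met |

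The first is the more realistic case: GM superiority together with a small, non-significant SCR gain.

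**5. How often H5 is reached.** It requires rejection of H1, H2, H3 and H4. For H3 at α₁ = 5%, SE = 1.5 × √(2/1700) = 0.0514. At a GMR of 0.85 the chance per strain is Φ(−0.1625/0.0514 − 1.96), about 1.5 × 10⁻⁷; at a GMR of 1.0 it is 2.5%. The wording therefore matters mainly if mRNA-1083 truly raises GM levels above the comparators.

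**The case against.** The strongest reply is that nobody would apply the rule literally. The null hypothesis in the same paragraph is comparative, and the criterion sentence itself speaks of superiority "compared to that of participants who received active comparator will be demonstrated by the lower bound of the 95% CI of the SCR". A single-arm rate set against 0% cannot test that null. The SAP defines the Cohort B SCR difference and already plans its 95% Miettinen-Nurminen interval, which matches the H5 level, since noninferiority uses the 97.5% interval. Cohort A, H6 and the protocol all use the difference. This stands: the intention is not in doubt, and misapplication is unlikely.

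The precedence clause can also be over-read. It covers methods that differ, SAP 1 confines SAP modifications to matters that are not principal, SAP 7 declares no change, and protocol 9 requires an amendment for a change to key hypotheses before unblinding. This also stands: an omitted word is not evidence of a new test. But the clause does prevent the protocol wording from settling the matter automatically.

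A reader might infer that Cohort B SCR superiority would be declared whatever the data show. The documents do not support that. H5 is reached only after noninferiority on all ten co-primary endpoints and GM superiority for all five strains, so the data can stop the sequence first. Nor is the literal criterion strictly always met: it fails if an arm has no seroconverters for a strain.

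What the reply does not remove is step 4 of the working: none of the earlier hypotheses tests SCR superiority.

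**Conclusion.** The concern holds as a drafting error in a confirmatory decision rule, with low practical risk. Read literally, and conditional on reaching H5, the criterion is met with probability about 1, against 2.5% per strain under the intended rule when the true rates are equal. It therefore does not control H5 at the stated two-sided 0.05 level, and it would open H6 without SCR superiority having been shown. The documents do not support reading it as a deliberate change of method.

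The figures assume 1,700 evaluable per arm and, for the intended-rule probabilities, a normal approximation. The 62% vs 60% and 54% vs 60% results are illustrations, not planning values. The literal result hardly depends on any of these, since one seroconverter per strain is enough.

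The same SAP paragraph says the response "is not superior to that in participants who received Fluarix HD + Spikevax", and protocol 9.2 makes the same slip. The Cohort B arm tables name Fluarix. This is a separate naming error that changes no analysis and adds no weight to the point.

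**What to change.** In SAP 4.2.2.2, insert the word difference after SCR in the H5 criterion. State its direction (mRNA-1083 + Placebo minus Fluarix + Spikevax), and keep the threshold of a lower 95% limit above 0% for all four influenza strains. Name the Miettinen-Nurminen 95% CI from SAP 6.3.1.3 as the interval to be used. In the same edit, change Fluarix HD to Fluarix in SAP 4.2.2.2 and in the Cohort B H5 text of protocol 9.2.

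The cost is a one-line SAP correction, best made before database lock and unblinding so that the rule is right on paper before anyone sees results. The protocol slip can wait for the next amendment. No sample size, power or alpha figure changes, and no new output is needed.
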